### **3.7. General Statistical Considerations for Safety Analysis**

If there are multiple assessments in a visit, the highest grade non-missing value within a visit will be used in the summaries, however all will be shown in the listings. If numeric data is beyond range of lab detectability and result is showed as “<XX” or “>XX” then the numeric XX value will be used for summary statistics.

There will be no specific strategy to deal with missing data i.e. it will not be imputed. A complete case analysis will be performed. For example when modelling the data based on a specific outcome only participants with complete data will be included.

Baseline is defined as last available measurement prior to dosing and post baseline abnormalities are included in the summary if the subject did not meet the abnormality criteria at baseline or toxicity grade at post baseline is higher than that on baseline.

All statistical analyses tables, listings and figures will be produced using STATA Version 16.0 or higher.

### **3.8. Newly notable abnormalities**

A newly notable laboratory abnormality is defined as an abnormality observed post baseline that meets the notable criteria in [Table 3](#) and that did not exist at baseline. Participants can still meet the criteria for newly notable laboratory if the baseline value is missing.

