### **2.3.3. Clinical safety laboratory measurements**

The incidence of newly notable (an abnormality observed post baseline that meets the notable criteria) grade 3 or 4 severity for laboratory parameters according to DMID grading. Participants are considered to have notable laboratory abnormalities if his/her response falls within the specified definitions (see Table 3 in §8.3.1) at least once during the treatment period.

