## **8.3. Clinical Evaluation**

### **8.3.1. Clinical Laboratory Evaluation**

A list of laboratory tests (haematology, clinical chemistry, and urinalysis) to be included in the analysis is presented in [§7.3 of the protocol](#). Laboratory assessments done by a central laboratory will be summarised in tables. All summaries will be based on the units provided by the central laboratory, no conversion will be done. The laboratory evaluations will be summarised for baseline, post-baseline, and change from baseline at week 8, end of treatment (week 17 or week 26), 52 week and 104 week FU.

Laboratory values outside normal ranges will be identified, and the number and percentage of participants with at least one post-baseline abnormality will be summarised in shift tables comparing the baseline results to each post-baseline timepoint for those participants with results at both timepoints.

The table below displays the general variables and thresholds of interest. Participants are considered to have notable laboratory abnormalities if his/her response falls within the specified definitions at least once during the treatment period.

Table 3:Notable Criteria for Laboratory Data

Lab Test Type	Laboratory Variable	SI Units
Liver	AST	>3 x ULN and ≤ 5 x ULN >5 x ULN and ≤ 8 x ULN >8 x ULN
	ALT	>3 x ULN and ≤ 5 x ULN >5 x ULN and ≤ 8 x ULN >8 x ULN
	Total Bilirubin	>2 x ULN
	Alkaline Phosphatase (ALP)	>2 x ULN
Chemistry Labs	Other: ALT or AST > 3 x ULN and total bilirubin > 2 x ULN ALT or AST > 3 x ULN and total bilirubin > 2 x ULN and ALP < 2 x ULN (potential Hy's law case)	
	Lipase	>2xULN to ≤5XULN >5xULN

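### SAP sections 3.7 and 3.8 disagree on whether a participant who already meets a Table 3 laboratory criterion at baseline is counted when the abnormality worsens

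*SAP*

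**What the plan says.** Three SAP sections bear on which laboratory abnormalities count as new.

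- **Section 3.8** is headed with the term and defines it. A newly notable abnormality is seen after baseline, meets Table 3, "and that did not exist at baseline". It has no clause for worsening. On missing data it adds: "Participants can still meet the criteria for newly notable laboratory if the baseline value is missing".
- **Section 3.7** gives the general rules for safety analysis. A post-baseline abnormality enters the summary "if the subject did not meet the abnormality criteria at baseline or toxicity grade at post baseline is higher than that on baseline". It also states: "A complete case analysis will be performed".
- **Section 2.3.3** names the secondary safety outcome as the incidence of "newly notable (an abnormality observed post baseline that meets the notable criteria) grade 3 or 4 severity", graded by DMID. Its bracketed gloss gives no baseline condition.

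Table 3, in section 8.3.1, sets the thresholds. AST and ALT have three bands (above 3 to 5, above 5 to 8, and above 8 x ULN). Lipase has two bands (above 2 to 5, and above 5 x ULN). Total bilirubin and ALP have one threshold each, >2 x ULN.

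The three notes to file appended to the SAP correct other wording and leave these sections untouched.

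**The concern.** Sections 3.7 and 3.8 are adjacent, yet they treat a participant who starts the trial above a threshold and gets worse on treatment in opposite ways. The result feeds a named secondary safety outcome, and the SAP gives liver safety its own tables, subgroup presentations, hepatotoxicity incidence and predictor analysis (section 8.2.8). Read literally, 3.8 leaves real on-treatment worsening out of the count. If two programmers each follow a different section, they can report different incidences from the same data, and the SAP would not show which of them is right.

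**Working it through.** The SAP states no figure to reproduce, so the check applies sections 3.7 and 3.8 to each possible combination of baseline and post-baseline values. *Notable* means meeting a Table 3 criterion for that test.

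| Baseline, then post-baseline | 3.7 | 3.8 |
|---|---|---|
| (a) Normal, then notable | counted | counted |
| (b) Abnormal but below the Table 3 threshold, then notable | counted | counted |
| (c) Notable, then notable at the same grade | dropped | dropped |
| (d) Total bilirubin or ALP >2 x ULN, then a higher grade | counted | dropped |
| (e) AST, ALT or lipase in a lower band, then a higher band and grade | counted | depends on reading |
| (f) Missing, then notable | cannot be determined | counted |

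**Row (d)** is the firm conflict. With one threshold there is no higher band that could be called a new abnormality. The abnormality existed at baseline, so 3.8 excludes it, while the grade rose, so 3.7 includes it.

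**Row (e)** turns on a point that 3.8 leaves open. If any notable ALT is one abnormality, the participant is dropped. If each band is its own abnormality, the participant is counted, in agreement with 3.7.

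**Row (f)** is a gap more than a contradiction. The worsening test in 3.7 needs a baseline grade, but 3.8 covers this case explicitly.

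**The grade limit in 2.3.3.** Suppose the abnormality that must be absent at baseline is taken to be the grade 3 or 4 abnormality itself. A participant below grade 3 at baseline who later reaches it is then new under both sections. A participant at grade 3 at baseline who reaches grade 4 is still counted by 3.7 and dropped by 3.8. The conflict narrows but remains. The SAP does not reproduce the DMID grades, so a given multiple of ULN for bilirubin or ALP cannot be assigned a grade from this document.

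**Size.** The SAP gives no baseline rates, so no estimate is possible. For orientation only, take these assumptions, none of which comes from the SAP: 2% to 5% of participants meet a criterion at baseline, and 10% to 20% of those worsen. The arm sizes are 150 (section 4) and 225 (section 7.3.4).

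- Low end: 0.02 x 150 = 3 participants; 3 x 0.10 = 0.3 per arm.
- High end: 0.05 x 225 = 11.25 participants; 11.25 x 0.20 = 2.25 per arm.

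This ignores the grade 3 or 4 limit and covers all tests, not only bilirubin and ALP. Under the same assumed rates, applying either restriction could only lower the figures.

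**The case against.** The strongest reply is that 3.8 is the specific definition and 3.7 only a general rule. Section 3.7 never uses the term newly notable or cites Table 3, and a programmer deriving that variable would start from 3.8. This has weight, but it does not settle the matter. Section 3.7 is addressed to safety analysis as a whole, speaks of abnormality criteria and toxicity grade, and exempts no laboratory summary. No order of precedence is stated.

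A second reply is that worsening is visible elsewhere. Section 8.3.1 has change-from-baseline summaries, shift tables and a potential Hy's law row. Section 8.2.8.3 reports AST or ALT at or above 3 x ULN without a baseline condition, and the third note to file provides liver enzyme plots. This is true and limits the harm. However, the plots are triggered by AST or ALT only, and none of these displays supplies the outcome in 2.3.3.

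Two stronger readings are tempting, and the SAP does not support them.

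- A reader might infer that 2.3.3 is a third, competing rule under which a value that merely persists from baseline is newly notable. Section 8.3.1 might seem to point the same way, since it says: "Participants are considered to have notable laboratory abnormalities if his/her response falls within the specified definitions at least once during the treatment period". But that sentence defines notable, not newly notable, and 2.3.3 keeps the word newly while 3.8 supplies the full definition. The natural reading is that 2.3.3 abbreviates 3.8.
- A reader might also infer that anyone abnormal at baseline is at risk of being dropped. Row (b) shows otherwise: a participant abnormal below the Table 3 threshold who becomes notable is counted under both sections.

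**Conclusion.** The conflict between 3.7 and 3.8 is real. For total bilirubin and ALP the two rules cannot both be followed when a participant already above the threshold worsens in grade. For AST, ALT and lipase the conflict depends on an unstated choice about bands. Section 2.3.3 adds looseness of wording but no separate rule that can be relied on.

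The consequence is limited. Sections 2.3 and 8 make safety descriptive with no inferential tests, so only a reported incidence changes. No efficacy conclusion or significance level is touched. The size cannot be computed from the SAP. The illustration above, from 0.3 to 2.25 participants per arm, rests wholly on assumed rates and supports no more than the view that the effect is probably small. The point still merits correction because it concerns a named safety outcome, one of the two rules omits on-treatment worsening, and the remedy is cheap.

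**What to change.** Make section 3.8 the single definition, consistent with 3.7. A post-baseline value is newly notable if either of these holds:

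1. the participant met no Table 3 criterion for that test at baseline; or
2. its toxicity grade, or its Table 3 band, is higher than at baseline.

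A missing baseline still counts, as 3.8 already provides. Sections 2.3.3 and 3.7 should refer to 3.8 in place of their own wording, and 2.3.3 should keep its limit to DMID grade 3 or 4.

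A bare cross-reference to 3.8 as it stands would remove the contradiction, but it would leave out the worsening that 3.7 sets out to capture. Naming both grade and band settles the AST, ALT and lipase question and gives bilirubin and ALP, which have no bands, a usable test.

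The cost is a short change of wording and one derivation rule. No new data are needed. The one small downside is that the reported count may rise slightly compared with a strict reading of 3.8.

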## **4. Sample Size**

For the primary endpoint, time-to-negative culture conversion at 8 weeks, 150 participants per arm (DS-TB participants) will provide more than 99% power (5% two-sided significance) to detect a hazard ratio (HR) of at least 2 (for 4BPaMZ vs. HRZE), assuming 50% of control participants are culture negative by 8 weeks. If only 25% of the control arm remain culture positive at 8 weeks, then this sample size will still retain more than 93% power to detect a HR of least 2. Note, non-randomised MDR participants will not be formally compared to any randomised group.

For the key secondary efficacy endpoint of clinical outcome at 12 months from randomisation, 150 participants per arm will provide 74% power at the two-sided 5% significance level based on assumptions using data from the largest most recently completed phase 3 TB treatment trial which used the same control arm [2]. That is, assuming 16% of participants in the control arm are unfavourable and 13% are unassessable at 12 months post randomisation. A non-inferiority margin of 12% is chosen and justified below.

This trial aims to demonstrate that the experimental regimen administered for 4 months to participants with DS-TB is not inferior to the standard 6-month control regimen using a non-inferiority margin of 12%, chosen based on the following rationale. The best estimate for the treatment effect (also known as M1 in guidance documents for non-inferiority trials) of the current standard treatment (HRZE) is derived from modern clinical trials of this treatment compared to historical, natural history trials. Based on the above reference, an estimate of the favourable rate observed with standard HRZE therapy of 84% is used. The WHO estimates that the case fatality rate for untreated smear positive pulmonary tuberculosis is 70%, and this estimate was confirmed in a systematic review in 2011 [3]. Therefore, an estimate of 30% for the favourable rate of placebo may be contrasted with the 84% favourable rate of the standard HRZE therapy. Based on these data, the best available point estimate for M1 (the overall treatment effect of HRZE, expressed as a risk difference) is 54%. A selection of 12% for M2 (the non-inferiority margin) would represent less than 25% of the point estimate of M1, thus assuring that the lower bound of the NI margin preserves more than 75% of the estimated treatment effect of the HRZE regimen.

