## 5. Analysis Populations

Analysis populations are:

- The **Intent to treat (ITT)** population, defined as all participants who were enrolled, whether or not they started treatment.
- The **Safety** population, defined as all enrolled participants who received at least one dose of study treatment. Participants will be analysed as to the treatment they actually received regardless of given allocation.
- The **Modified intent to treat (mITT)** population, defined as all participants who were enrolled and started treatment, excluding any late screening failures.
- The **TB-specific modified intent to treat (TB-mITT)** population, defined as the mITT population with additional exclusions (see below).
- The **Per-protocol (PP)** population, defined as the TB-mITT population with additional exclusions (see below).

For ITT, mITT, TB-mITT and PP; participants will be analysed as to the treatment they were randomised to receive.

For short-term culture conversion endpoints, only the mITT population will be examined.

The TB-mITT population is unique to the TB field and is outlined here (with further details provided in [Appendix §13.3](#)). TB-mITT is a key analysis that has been used in the literature of long-term outcome trials of durable cure in TB, although it has generally been referred to simply as the ‘mITT analysis’. This analysis excludes participants based on data collected post-randomisation. A true mITT analysis, as recognised by regulatory authorities, does not exclude any participants due to missing data post-enrollment.

Thus, for the long-term endpoint of durable cure, the TB-mITT analysis will be considered primary for the purposes of publication, to allow comparison with the rest of the literature in the TB field. However, for regulatory purposes, we recognise that regulatory agencies will consider the mITT analysis primary.

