### 6.2. Long term endpoints

#### Favourable status (all analysis populations)

Participants with culture negative status at the time of the endpoint (at 12 or at 24 months), who have not already been classified as having an unfavourable outcome and whose last positive culture result (“isolated positive culture”) was followed by at least two negative culture results. For participants who are missing culture status at the 12 month endpoint but who have a culture result at a future timepoint will be considered culture negative status at 12 months if both the previous and future culture results are negative.

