#### 6.2.1. mITT Population

##### 6.2.1.1. Unassessable status (late exclusions)

1. Participants enrolled and later found to be ineligible because of a protocol violation at enrolment (based on data collected prior to enrolment).

2. Participants without culture confirmation of M.tb at Day 1 (baseline) sputum samples (or screening or out to Week 4 if the baseline is contaminated or negative). These participants will be late exclusions from the study.

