#### **6.2.1.2. Unfavourable status**

Participants in the mITT analysis population who do not reach the time of the endpoint (12 or 24 months depending on the endpoint) or who are not culture negative status at the time of the endpoint (12 or 24 months) and whose last positive culture result (“isolated positive culture”) was not followed by at least two negative culture results.

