#### **6.2.2. TB-mITT Population**

##### **6.2.2.1. Unassessable status (additional exclusions from mITT)**

In addition to those excluded from the mITT analysis (see §6.2.1.1), the following participants will be excluded:

1. Participants who, having completed treatment, are lost to follow-up or withdrawn from the study, their last status being culture negative and their last positive culture result (“isolated positive culture”) followed by at least two negative culture results at different visits (at least 7 days apart, without an intervening positive culture).
2. Women who become pregnant during treatment and stop their allocated treatment.
3. Participants with suspected/confirmed COVID-19 during treatment and who stop their allocated treatment.
4. Participants who died during treatment from violent or accidental cause (e.g. road traffic accident). N.B.: This does not include death from suicide, which will be considered an unfavourable outcome.
5. Participants who died during follow-up (after the end of treatment) with no evidence of failure or relapse of their TB, their last status being culture negative and their last positive culture result (“isolated positive culture”) followed by at least two negative culture results at different visits (at least 7 days apart).
6. Participants who, after being classified as having culture negative status are deemed culture positive and are infected with a new strain that is different from that with which they were originally infected. Reinfection will be defined specifically as a participant infected with a strain that is genetically different from the initial strain (see [Appendix §13.2](#)).

7. Participants who are able to produce sputum at the endpoint visit, but whose endpoint visit sputum samples are all contaminated or missing, who cannot be brought back for repeat cultures, provided their last positive culture was followed by at least two negative cultures. N.B.: This does not apply to participants who are unable to produce sputum at the given endpoint (see [§3.1.4](#)), or to participants who are able to be brought back subsequently and produce negative cultures.

Participants in categories 1-7 above who have already been classified as having an unfavourable outcome will not be excluded.

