In a study conducted by the IUATLD the published failure/relapse rates 12 months after stopping treatment based on 1044 assessable participants were 5% for the control regimen and 10% and 14% in each of the experimental arms. If the 311 unassessable participants were considered to have an unfavourable outcome these rates would have increased to 24%, 32% and 35%, respectively. The 311 unassessable participants were not evenly distributed across the three trial arms. There were 42 deaths, of which 20 occurred in one of the experimental arms (the more efficacious of the two) and 11 in each of the other, a difference which was not considered to be due to the treatment, but due to chance. There were also imbalances among those without a bacteriological assessment (7 in one arm versus 19 and 22 in the other two arms) and in the distribution of losses to follow-up.

Hence the adaptation to this situation in publications, generally replacing what is usually considered mITT analyses in the TB field with TB-mITT analyses.

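### The 90% and 86% powers at 225 per arm remove 13% as loss to follow-up and name no population; mITT keeps such losses as unfavourable, which gives about 82% and 78%.

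*SAP*

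**What the plan says.** - §4 gives 74% power at 150 per arm for the 12-month non-inferiority comparison (margin 12%, two-sided 5%), "assuming 16% of participants in the control arm are unfavourable and 13% are unassessable at 12 months post randomisation". It states no analysed number, variance method or population.
- Table 2 in §7.3.2 sets out the final stage of the extended design: one-sided 2.5%, power 90%, control favourable rate 84%, true difference 0, and a 13% rate labelled as attrition and loss to follow-up.
- The program output in §13.4 shows 225 recruited and 196 analysed per arm. It says the recruited number allows for the loss-to-follow-up rate. The pairwise power is 0.860.
- §7.3.4 says that 225 per arm adequately powers the new primary endpoint, with 86% overall. §7.3.1 names mITT for the interim endpoint but names no population for the 12-month endpoint.
- §2.2 plans the 12-month comparison in mITT, TB-mITT and PP.
- §5 makes TB-mITT primary for publication and adds that "for regulatory purposes, we recognise that regulatory agencies will consider the mITT analysis primary". It also says: "A true mITT analysis, as recognised by regulatory authorities, does not exclude any participants due to missing data post-enrollment".
- §6.2.1.2 classes as unfavourable "Participants in the mITT analysis population who do not reach the time of the endpoint". §6.2.1.1 removes only participants found ineligible on pre-enrolment data and those without culture confirmation ("These participants will be late exclusions from the study").

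**The concern.** The three populations treat losses differently, so a 12-month power means little until its population is named. The calculation for 225 per arm takes the 13% out of the denominator, while the mITT rule keeps losses in and counts them as failures. That raises the unfavourable rate and therefore the variance of the difference.

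The extension to 225 is justified by the power it gives to an outcome that would then become primary. If the 13% are losses, the chance of missing true non-inferiority in mITT is about 22% (100 − 78), not the 14% (100 − 86) that a reader would take from §7.3.4. The SAP gives no mITT power.

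**Working it through.** **Inputs.** Control unfavourable rate 16%, margin 0.12, 13% lost or unassessable, 150 or 225 per arm (§4, Table 2, §7.3.4); one-sided 0.025 at the final stage; stage 1 power 0.95 (Table 2, §13.4). Assumed: equal loss in both arms, no true difference, and 16% applying to the remaining 87%.

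**Formula.** Power = Φ(0.12 / √(2p(1−p)/n) − 1.96), with p the unfavourable rate and n the number analysed per arm.

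**Step 1: reproduce the 90% and 86%.** With p = 0.16 and n = 196: √(0.2688/196) = 0.0370; 0.12/0.0370 = 3.240; Φ(1.280) = 90.0%. Overall power is 0.95 × 0.900 = 85.5% if the stages are independent, and 86.0% with a correlation of about 0.22, as implied by the positive predictive values of 95%. Both stated figures reproduce with 196 analysed.

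**Step 2: mITT at 225, all of the 13% losses.** p = 0.87 × 0.16 + 0.13 = 0.2692 and n = 225. √(0.3935/225) = 0.0418; 0.12/0.0418 = 2.870; Φ(0.910) = about 81.8% final-stage. Overall power is 77.8% to 78.5% for a correlation between 0 and 0.22. A simulation of 400,000 trials with Wald intervals gave 81.9% final-stage, and 90.0% when the 13% are excluded.

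**Step 3: the 74% at 150.** Two routes lead to it.
- Removing the 13%: n = 0.87 × 150 = 130.5 gives 75.3% by the formula above, or 73.6% with the Farrington-Manning variance.
- Analysing all 150 with the variance at the null (16% against 28%): (0.12 − 1.96 × √(0.336/150)) / √(0.2688/150) = 0.643, and Φ(0.643) = 74.0%.

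The text does not say which was used.

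**Step 4: mITT under different compositions of the 13%.** Overall figures use a correlation of 0 to 0.22.

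| The 13% consist of | p | 150 per arm | 225, final stage | 225, overall |
|---|---|---|---|---|
| all losses | 26.9% | 64.9% | 81.8% | 77.8–78.5% |
| half late exclusions, half losses | 21.8% | 68.2% | 84.6% | 80.4–81.0% |
| all late exclusions | 16.0% | 75.3% | 89.9% | 85.5–85.9% |
| half favourable at month 12, half losses | 20.4% | 73.2% | 88.4% | 84.0–84.6% |

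Only the first row follows from the loss-to-follow-up label. The others are scenarios, because the SAP does not give the composition.

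**The case against.** **There is no arithmetic error.** This stands. The 90% and 86% are right for an analysis that drops the 13%. The fault is that no such analysis is named and that mITT is not one.

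**§4 says unassessable, not lost.** This stands for the 74%. In the mITT subsections that word heads the list of late exclusions, and if all 13% were late exclusions, mITT power would be about 75% at 150 and 90% / 86% at 225. It does not rescue the 225 design, where Table 2 and §13.4 both call the 13% loss to follow-up.

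**The population can be inferred as TB-mITT.** This stands in part. §6.2.2.1 excludes "Participants who, having completed treatment, are lost to follow-up or withdrawn from the study, their last status being culture negative", so removing losses looks like that analysis. But §6.2.2.2 item 7 counts losses before the end of treatment as unfavourable in TB-mITT too, so the match is incomplete and the SAP never states it.

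**The composition is unknown, so any mITT range is arbitrary.** This stands against treating 65–73% at 150, or 78–85% overall at 225, as the full range. Those upper ends need half of the 13% to be favourable, a split found nowhere in the SAP. With only a quarter unfavourable and the rest favourable, power would be 78.7% at 150 and about 92% final-stage at 225, above the stated values. If 16% and 13% are both shares of all participants (p = 29%), it falls to 62.9% at 150 and about 76–77% overall at 225.

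**The other trial in §13.3 says nothing about this 13%.** Agreed. It shows that counting unassessable participants as unfavourable can raise rates sharply, but it is no evidence of the composition here.

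**mITT power may be in the protocol.** Possibly. The SAP's own 90% and 86% would still need a population beside them.

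**Conclusion.** The point holds for the 90% and 86%. They describe an analysis of 196 of 225 per arm. Under the SAP's own label for the 13%, mITT power is about 82% final-stage and 78% overall, a shortfall of about 8 points on each. This rests on equal loss in both arms, no true difference, and all 13% failing to reach month 12. The 90% would hold for mITT only if nearly all of the 13% (about 97%) were late exclusions, or if about 61% reached month 12 and counted as favourable with the rest losses. Neither fits a loss-to-follow-up label.

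For the 74% the finding is narrower: the description of the 13% must be reconciled and the basis stated. A reader might infer that the 74% also excludes the 13% and so is equally wrong for mITT. The document does not support that, because §4 gives no analysed number and 74.0% also arises with all 150 analysed. Nor does it support a claim that the sample size was miscalculated, or any claim about TB-mITT power.

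**What to change.** 1. In Table 2 and §7.3.4, and in a note beside the output in §13.4, state that 90% and 86% apply to an analysis that excludes the full 13% (196 of 225 per arm). Name that population, and limit the statement in §7.3.4 about adequate power to it.
2. In §4, state the analysed number, variance method and population behind the 74%. Use one description of the 13% in §4 and Table 2, and say what it comprises: late exclusions, losses, deaths, missing endpoint samples.
3. Add mITT power with its assumption: about 65% at 150, and 82% final-stage and 78% overall at 225, if all 13% are losses; about 75%, and 90% and 86%, if all are late exclusions. Show any intermediate split as a scenario, not as a full range.

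This takes a few sentences and a handful of figures. Enrolment, margin, analysis and decision rule stay as they are. The cost is a less favourable stated power for mITT.
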